## 7.7 Visit Windows

Study visits will include Screening, Day 0, and nominal week or month indicated in the table below. Visit windows will be used in data listings, summaries and analyses and will be based on study day of the observation, defined as:

$$\text{study day} = \text{date of observation} - \text{Day 0 date}$$

Visit windows per protocol and to be used in listings, summaries and analyses are as follows:

Nominal Visit	Nominal Day	Min Day Per Protocol	Max Day Per Protocol	Min Day for Analyses	Max Day for Analyses
Week 2	14	11	17	1	29
Week 6	42	33	47	30	61
Month 3	90	83	97	62	153
Month 6	180	166	194	154	275
Month 12	360	330	390	276	427

where cell entries are study days as defined above. For example, per protocol the Month 3 visit will occur between 83 and 97 days post infusion (Day 0), but for purposes of listings, summaries

and analysis all observations dated between 62 and 153 days post infusion will be included in the Month 3 visit window.

Efficacy assessments that occur too late to be included in the Month 12 analysis window will be included in “last observation” analyses (see [Section 10](#)).

For ITT summaries and analyses, study day will be defined as:

$$\text{study day} = \text{date of observation} - \text{randomization date} - X$$

where X is the number of days between randomization and Day 0.

For example, for a subject who received IP 5 days after randomization and who had an assessment 65 days after randomization, the study day for that assessment would be 60 and the assessment would therefore fall into the Week 6 analysis window.

In addition, visit windows based on time of data collection will be defined for assessments done during the 24 hours post IP administration as follows:

Nominal Visit	Nominal Hour	Min Hour for Analyses	Max Hour for Analyses
8 Hours Post	8	4.01	12.00
16 Hours Post	16	12.01	20.00
24 Hours Post	24	20.01	28.00

If multiple valid, non-missing observations exist within a given window, the observation to be used will be:

1. the observation closest to the nominal visit day in question, or
2. the latest observation if the multiple observations are equidistant from the nominal visit day, or
3. the average (arithmetic or geometric, as appropriate) of the observations if the multiple observations have the same actual time point. In instances of multiple observations with the same time point from different laboratories, only observations from the central laboratory will be used.

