### Post-infusion (D0-D1):

- Serial collection of vital signs (temperature, HR, BP, and RR) every 8 hours ( $\pm$  30 minutes) from the end of the infusion.
- Cardiac Physical Examination
- 12-lead ECG
- Serial venous collection for cardiac enzymes (Troponin and CK-MB)
- Venous blood will be collected for clinical laboratory tests: chemistry, hematology, and urinalysis

Following intracoronary infusion, subjects will be observed in the hospital for 20-24 hours with continuous cardiac (telemetry) monitoring. Troponin and CK-MB laboratory studies will be monitored every 8 hours ( $\pm$ 30 minutes) from the end of the infusion. A total of three

sets of cardiac enzymes will be evaluated to rule out cardiac injury during the post-infusion hospital stay through discharge. If the subject is discharged prior to 24 hours, cardiac enzymes will be drawn just prior to discharge.

*Day 1 Prior to Hospital Discharge:*

- Review of concomitant medications
- Adverse event assessment
- Physical assessment (chest pain, infusion/arterial puncture site(s))
- Review of lab results and 12-lead ECG

Prior to discharge from the hospital, a physical assessment will be performed which will include chest pain assessment, review of laboratory results, 12-lead ECG, and arterial puncture site as well as assessment of adverse events. In the absence of serious adverse events, subjects will be discharged per standard of care practice.

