 For eligible subjects randomized to the usual care arm, Day 1 is established as 8 days after the date of randomization, without an actual Day 1 visit. All study subjects initiate 72-hour continuous cardiac rhythm monitoring on Day 1.

 If standing height cannot be measured, height will be calculated using a measurement of ulna length (Gauld et al 2004).

 Serology includes HIV and hepatitis testing

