#### 7.2.1 Tables and Figures

- Tables and figures will present data summaries and/or analyses for the appropriate study population; e.g., summaries of safety parameters will be shown for the safety population only.
- Treatment group order in tables and figures will be usual care, CAP-1002, and “All Subjects.” Note: not all tables and figures will show data summarized for “All Subjects.”
- Tables and figures will present summaries/analyses by study visit window, if applicable.
- Table column headers and figure legends will include subgroup sample sizes.

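### SAP 7.7 has no Day 1 visit and no rule separating hour windows from day windows, so Day 1 rhythm recordings are summarised as Week 2 and some early CAP-1002 values can be misplaced

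*SAP*

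**What the plan says.** SAP 7.7 assigns observations to visits by study day, defined as observation date minus Day 0 date: "Visit windows will be used in data listings, summaries and analyses and will be based on study day of the observation". The list of visits is closed: "Study visits will include Screening, Day 0, and nominal week or month indicated in the table below". The Week 2 row reads "Week 2 14 11 17 1 29", that is, nominal day 14, protocol days 11 to 17, analysis days 1 to 29. SAP 7.2.1 carries this into the outputs: "Tables and figures will present summaries/analyses by study visit window, if applicable".

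A second set of windows is then added: "visit windows based on time of data collection will be defined for assessments done during the 24 hours post IP administration". These are 8 h (4.01-12.00), 16 h ("16 Hours Post 16 12.01 20.00") and 24 h (20.01-28.00). One tie-break follows for all windows: closest to the nominal visit day, then the latest if equidistant, then an average for identical time points.

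On the protocol side, Appendix 1 footnote 3 states: "All study subjects initiate 72-hour continuous cardiac rhythm monitoring on Day 1". Section 6.7 and Table 3 place recordings at Screening, Day 1, Week 6, Month 6 and Month 12, and none at Week 2. After infusion, subjects stay 20-24 hours with three enzyme sets at 8-hour intervals (±30 minutes), and "If the subject is discharged prior to 24 hours, cardiac enzymes will be drawn just prior to discharge". Usual-care subjects have no Day 0 or Day 1 visit (Appendix 1 footnote 1; Appendix 2).

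**The concern.** Safety is the primary objective, and the first days after infusion are the period of most interest. SAP 9.7 summarises continuous monitoring by study visit, and SAP 14 sends it to the DSMB. If the recording that starts the day after infusion appears in a Week 2 column, a reader will take early rhythm findings for findings two weeks later.

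The other two gaps concern values collected after infusion. Without a rule on precedence, an acute laboratory, ECG or vital-sign value could fill a Week 2 cell. Usual care has no samples from which this could happen, so the error would be one-sided. Those Day 0 and Day 1 laboratory values are also local (protocol 6.5.2), and the SAP's preference for central-laboratory results applies only to observations at the same time point. Finally, a tie-break worded in days does not clearly work inside a window measured in hours, which matters when two enzyme sets fall in the same window.

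**Working it through.** **Check of the rules as read.** The SAP's own example, IP 5 days after randomization and an assessment 65 days after it, gives 65 − 5 = 60, inside the Week 6 window (30-61). This reproduces the SAP's answer. The Month 3 protocol range, 90 ± 7 = 83 to 97, also agrees.

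**1. Day 1 rhythm recording.** It starts on study day 1 and, at 72 hours, ends about day 4. Days 1 to 4 all lie in 1-29, so the label is Week 2 whichever date is used. The ITT definition (observation date − randomization date − X, with X the days from randomization to Day 0) gives the same study day. No Week 2 recording is scheduled, so nothing displaces it. The hour windows do not help: they cover only the 24 hours after IP, and usual care receives none.

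**2. Hour windows against day windows.** Draws at 8, 16 and 24 h (±0.5 h) each fall in their intended hour window. If infusion ends between 09:00 and 15:00 (assumed), the 8 h set has study day 0, while the 16 h and 24 h sets have study day 1 and so also meet the Week 2 day rule. Under the tie-break, a Day 1 value lies |1 − 14| = 13 days from nominal:

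| Date of Week 2 value | Distance from day 14 | Value used |
|---|---|---|
| day 11-17 | 0-3 | Week 2 value |
| day 26 | 12 | Week 2 value |
| day 27 | 13 (tie) | latest, so Week 2 value |
| day 28, 29 | 14, 15 | Day 1 value |
| missing | – | Day 1 value |

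Illustration only: assume that each of 12 infused subjects independently has a 5% or 10% chance of no usable Week 2 sample, and that dual assignment is always programmed. The chance of at least one such case is 1 − 0.95^12 = 0.46 or 1 − 0.90^12 = 0.72. If one value were 5 or 10 times the other eleven (assumed), the arm mean would be (11 + 5)/12 = 1.33 or (11 + 10)/12 = 1.75 times its usual level. The documents give neither the missing rates nor the outlier sizes.

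**3. Pre-discharge enzyme set.** The 16 h set is due at 15.5-16.5 h. A pre-discharge draw at or before 20.00 h falls in 12.01-20.00, the same window; from 20.01 h it falls in the 24-hour window. With a 20 h minimum stay, discharge must come no later than 20 h plus the lead time between draw and discharge. For assumed leads of 0.25, 0.5 and 1 h, and discharge spread evenly over 20-24 h, the share affected is 0.25/4 = 6%, 0.5/4 = 12.5% and 1/4 = 25%.

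Which set survives depends on how the tie-break is read:
- In hours: the 16 h set is at most 0.5 h from nominal and a draw at 19.5-20.0 h is 3.5-4 h away, so the 16 h set is kept.
- In days, as worded: for infusions ending 09:00 to 17:00 both draws share a calendar date, so they are equidistant. The later, pre-discharge set is kept.

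Either way, one of the three sets leaves the by-time summary and the 24-hour cell is empty.

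**The case against.** The strongest reply is that little is lost. SAP 7.2.2 lists all data collected, and SAP 9.7 lists recordings with start and stop times. Peak troponin and CK-MB elevation is a separate assessment not tied to a window (SAP 2.3.1). MACE within 72 hours is adjudicated (SAP 9.1), and so is VT of 30 seconds or longer. All of this stands and limits the consequences to by-visit and by-time summaries. On rhythm, the error is one of label, equal in both arms, and may stem from SAP Appendix A, which still shows a 24-hour ambulatory ECG under the infusion visit. That explains the gap but does not close it, because the written rule still yields Week 2.

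Two stronger readings are tempting. A reader might infer that CAP-1002 post-infusion values in general fall into Week 2. They do not: the hour windows cover 4.01-28.00 h, SAP Appendix B plans separate post-infusion figures for cardiac biomarkers, and any Week 2 value dated day 11-17 displaces a Day 1 value. A reader might also infer that the last enzyme set is discarded for early discharges. The text does not say so. The day-worded tie-break keeps the later set, and pre-discharge draws after 20.00 h are filed correctly as 24 h.

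One could also object that moving the hour boundary to 18 h is a matter of taste. It is one workable option; what matters is that the assignment be explicit.

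**Conclusion.** The point holds in three parts of unequal weight.

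- **Rhythm recording:** certain on the SAP's wording, and affects every subject with a Day 1 recording, among approximately 24 and at most 30 randomized. It is a wrong time label in safety tables, without loss of data.
- **Day 1 values standing as Week 2:** conditional on a Week 2 value that is missing or dated day 28-29, and on a programmer not adding an exclusion that the SAP does not state. For laboratory tests, ECG and vital signs it can occur only in the CAP-1002 arm. The 46%/72% and 33%/75% figures illustrate scale under assumed inputs and are not estimates.
- **Enzyme set at the 20 h limit:** a narrow boundary case. One set drops out of the by-time summary and the 24-hour cell is empty, but the SAP does not settle which set drops.

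None of this threatens the adjudicated events, the listed data or the peak enzyme assessment. It is worth correcting because the trial is open-label and these choices should not be left to programming after data are seen.

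**What to change.** In SAP 7.7:

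1. Add a Day 1 row for the home rhythm recording (start on study day 1, short upper limit) and open the Week 2 analysis window after it.
2. State that an observation assigned to an hours-post-infusion window is not eligible for a study-day window.
3. Word the tie-break in hours for the hour windows.
4. Assign the pre-discharge enzyme set explicitly to the last post-infusion time point, for example by moving the 16/24-hour boundary from 20.00/20.01 h to 18.00/18.01 h. This fits the protocol's ±30 minute draw window: the 16 h set is due by 16.5 h, or by 17 h if the tolerance accumulates over two intervals (16 + 2 × 0.5).

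The cost is a few lines in the SAP and the matching programming, with no new data. The drawback is that some values labelled 24 hours will have been drawn as early as about 20 h; a footnote giving the actual range of draw times would cover that.

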## **7.11 Early Termination Procedures**

Every reasonable effort will be made to retain subjects in the study. In the event that a subject must be withdrawn from the study early, study personnel should attempt to obtain testing and data required for the 12 Month Visit (see Section 7.8) as well as the reason for withdrawal, if known. A Cardiac MRI will be conducted provided the subject's most recent study-related Cardiac MRI was conducted at least three months (i.e., 12 weeks) prior to the Early Termination Visit.

If the subject permits, he or she should be contacted by study personnel at the time of their usual study visits (and annually through 5 years post-infusion), as described in the protocol.

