### **9.4 Safety Laboratory Evaluations**

Specific laboratory evaluations to be performed are detailed in Appendix 2 of the protocol. Listings of safety laboratory evaluations will include study visit, date and time of collection, normal ranges, observed values with out-of-range values flagged, and changes from baseline. Separate series of listings will show out-of-range observations.

Observed values and changes from baseline will be summarized by study visit. A separate series of summaries will show incidence of out-of-range observations by study visit. Shift tables will summarize shifts from one out-of-range category at baseline to another out-of-range category at each subsequent study visit and will include p-values for treatment group differences.

Listings and summaries will be done separately for each of the following laboratory evaluations or groups of evaluations:

- Serum chemistry (basic metabolic and comprehensive hepatic panels)
- Hematology
- Urinalysis
- Glycosylated hemoglobin (HbA1c)
- Cardiac (troponin I, troponin T, CK-MB)
- Immunogenicity (HLA, DSA, enzyme-linked immunosorbent spot (ELISPOT))
- Exploratory biomarkers, if available

For DSA, the raw data will be provided by the core laboratory and a listing of HLA antibodies and specific alleles will be provided to the independent clinical immunologist to make the final determination of which are DSA caused by sensitization to the donor cells, and which are non-specific changes that are not due to donor-specific sensitization. Any summary tables or analyses of DSA will be based on DSA as adjudicated by the independent clinical immunologist.

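### Shift tables as worded leave out subjects in range at baseline, and the closest-to-nominal rule can drop Early Termination and unscheduled values from by-visit safety tables

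*SAP*

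**What the plan says.** **Analysis visits (SAP 7.7).** "Study visits will include Screening, Day 0, and nominal week or month indicated in the table below". The table lists Week 2, Week 6, Month 3, Month 6 and Month 12, with no row for Early Termination or unscheduled visits. The analysis windows join without gaps from day 1 to day 427 and are much wider than the protocol windows. The protocol window for Month 3 is days 83 to 97, yet "all observations dated between 62 and 153 days post infusion will be included in the Month 3 visit window".

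**Choice of value (SAP 7.7).** "If multiple valid, non-missing observations exist within a given window, the observation to be used will be" the one nearest the nominal day. If two are equally near, the later is used; values at the same time point are averaged. SAP 9.4 makes no exception for safety tables.

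**Laboratory tables (SAP 9.4).** "A separate series of summaries will show incidence of out-of-range observations by study visit". Then: "Shift tables will summarize shifts from one out-of-range category at baseline to another out-of-range category at each subsequent study visit". SAP 9.5 and 9.7 also summarise vital signs and ECG by study visit. Appendix B lists no worst-value or any-time post-baseline table.

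**The extra data exist.** When a subject is withdrawn early, Protocol 7.11 says that "study personnel should attempt to obtain testing and data required for the 12 Month Visit", and Protocol Appendix 1 has an Early Termination column. SAP 8.8 counts unscheduled visits among the visit dates.

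**Late values.** The 'last observation' analyses in SAP 7.7 and 10 concern efficacy assessments made too late for the Month 12 window.

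**Protocol commitment.** Protocol 9.5.3 compares each post-treatment laboratory value with baseline. SAP 15 declares only the mITT definition as a deviation.

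**The concern.** Safety and tolerability are the primary objective, with about 12 subjects per arm. A laboratory shift table is meant to show who moved from normal to abnormal. Taken literally, SAP 9.4 tabulates only subjects who were abnormal at the start.

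The window rule works in the same direction. A result taken at withdrawal, or because something looked wrong, competes with a routine result for one place, and distance from the nominal day decides which is used. The value itself plays no part. With 12 subjects in an arm, one abnormal value lost from a by-visit table changes its incidence by 1/12 = 8.3 percentage points.

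**Working it through.** The plan gives no figure to reproduce here. The check counts what its rules include and exclude.

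**1. Shift tables.** With categories low, normal and high there are 3 × 3 = 9 baseline-to-later cells. The SAP 9.4 wording covers low-to-low, low-to-high, high-to-low and high-to-high: at most 4 of 9, or 2 of 9 if the later category must differ. Normal-to-low and normal-to-high are outside it. The documents give no share of subjects out of range at baseline. Assuming 10% to 50% for a given test, 12 × 0.10 = 1.2 to 12 × 0.50 = 6 subjects per arm could enter the table, so 6 to 10.8 could not.

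**2. Window widths (SAP 7.7 table), in days.** The last column counts the window days on which an extra result is certain to lose, wherever the scheduled visit falls in its protocol window.

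| Visit | Analysis | Protocol | Ratio | Certain to lose |
|---|---|---|---|---|
| Week 2 | 29 | 7 | 4.1 | 22 (76%) |
| Week 6 | 32 | 15 | 2.1 | 13 (41%) |
| Month 3 | 92 | 15 | 6.1 | 77 (84%) |
| Month 6 | 122 | 29 | 4.2 | 93 (76%) |
| Month 12 | 152 | 61 | 2.5 | 91 (60%) |

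**3. Early Termination, parameters measured at every visit.** Assume that earlier visits took place on their nominal days. Days lost per window = window maximum − nominal day:

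- Week 2: 29 − 14 = 15
- Week 6: 61 − 42 = 19
- Month 3: 153 − 90 = 63
- Month 6: 275 − 180 = 95

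The sum is 192, and 192/360 = 53.3%.

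The SAP 7.7 table puts Week 6 at day 42, but Protocol 7.5 and SAP Appendix A put it at day 40. With a day-40 visit, two days from nominal, termination on day 43 is nearer. Day 44 ties and wins as the later value. The Week 6 loss becomes days 45 to 61, or 17 days. The total is 15 + 17 + 63 + 95 = 190 of days 1 to 359 (52.9%). On the other 169 days (47%) the Early Termination value is used, under a nominal visit label.

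**4. Parameters measured less often (Protocol Appendix 1).** A value is lost only if a scheduled value of the same parameter competes.

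- Troponin and CK-MB are not scheduled at Week 6 or Month 3: 15 + 95 = 110 days.
- PUL, spirometry, 6MWT and quality of life are not scheduled at Week 2: 17 + 63 + 95 = 175 days.
- Weight is scheduled after baseline only at Months 6 and 12: 95 days.
- MRI is repeated at Early Termination only if the last study MRI was at least 12 weeks (84 days) before. After a day-180 scan the earliest is 180 + 84 = day 264, so days 264 to 275 are at risk: 12 days.

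**5. MRI before day 154.** Such a scan falls in the Month 3 window or earlier. The model in SAP 10 uses baseline, Month 6 and Month 12. If it is the only post-baseline scan, the subject meets the SAP 6 mITT definition but has both modelled changes missing, a case that SAP 10 says maximum likelihood cannot handle.

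**The case against.** The strongest reply is that little is truly lost.

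- **Adverse event route.** Under Protocol 7.13.6 and 7.13.7, an abnormal result that calls for closer follow-up or further investigation is clinically significant and is documented for adverse event reporting. The TEAE, SAE and discontinuation tables in SAP 9.2 have no visit windows. This stands, with a limit: Protocol 7.13.7 leaves out findings associated with the disease unless the investigator judges them more severe than expected, and the trial is open-label.
- **New abnormalities are still counted.** The by-visit out-of-range tables do not depend on baseline status. This also stands, for the selected value. They do not separate new from pre-existing abnormality.
- **Drafting slip.** Appendix B titles the tables simply as shifts from baseline, so the SAP 9.4 wording may be a slip. That is possible, but a programmer following the text would build the wrong table.
- **The rule is objective and treats both arms alike.** This stands, and is a reason to keep it for by-visit means. A worst-value table needs care. Only CAP-1002 subjects have Day 0 and Day 1 local laboratory draws, and Day 1 lies inside the Week 2 analysis window. Including them would raise that arm's out-of-range rate through extra draws alone.

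A reader might infer that the safety tables as a whole miss the values most likely to show harm, that dropped values appear only in listings, or that 53% of all Early Termination data are lost. The documents support none of these. The adverse event route exists, Early Termination values are kept on about 47% of days, and the 53% applies only to parameters measured at every visit. That withdrawal or for-cause results best show harm is a reasonable inference, but the documents do not state it. Protocol 7.10 also lists reasons for withdrawal unrelated to safety.

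**Conclusion.** Two gaps hold. The SAP 9.4 shift tables, as worded, do not tabulate normal-to-abnormal shifts. The SAP 7.7 rule can drop Early Termination and unscheduled abnormal values from by-visit laboratory, vital-sign and ECG tables, and no worst-post-baseline table makes up for it.

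The exposure is about 190 of 360 possible termination days for parameters measured at every visit, and fewer for the others. These are counts of days and do not predict how many subjects are affected. They assume that visits took place on their planned days; the 53% is a loss rate only if every termination day is equally likely. The documents give no withdrawal rate, and SAP 10 expects very few missing observations, so the number of values affected may be small. The change is still worth making, because safety is the primary objective and one value is 8.3 percentage points of a 12-subject arm.

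**What to change.** 1. Reword SAP 9.4 so that shift tables use low, normal and high at baseline against low, normal and high later, with in-range baselines included.
2. Keep the closest-to-nominal rule for by-visit means. Add out-of-range incidence and shift tables on the worst post-baseline value (lowest and highest, as the test requires), using all scheduled, unscheduled and Early Termination results. For the between-arm comparison, leave out the Day 0/1 post-infusion local laboratory draws taken only in the CAP-1002 arm, and summarise them separately.
3. Extend the existing 'last observation' efficacy analysis to Early Termination assessments, including an MRI before day 154. A separate Early Termination efficacy time point is a matter of preference and is not needed.

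The cost is SAP wording and some extra programming, with no new data. Out-of-range percentages will be somewhat higher, and part of any difference between arms may reflect unequal numbers of unscheduled draws. Showing the number of draws per subject by arm beside these tables would let a reader judge that.
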